The use of intravesical gentamicin sulfate as a clinical strategy to prevent UTIs has been shown to be successful and safe in treating and suppressing recurrent UTIs in both adults and children (41-43). The administration of aminoglycosides (having primarily bactericidal activity against Gram-negative aerobes and facultative anaerobic bacilli) intravesically permits the use of high concentrations of antimicrobial solution targeting a local pharmacological effect while limiting systemic adverse effects such as nephrotoxicity, or impacting gastrointestinal flora. This approach helps prevent the development

of antimicrobial resistance. From the various aminoglycosides, gentamicin remains the best studied of these agents for bladder washout use and is the only intravesical treatment that has been shown to be safe and effective in both the prevention and treatment of UTIs (44, 45).

II. General Experimental Design

A. Objectives: The purpose of this feasibility study is to address the prevalence of chronic, recurrent urinary tract infections in adults living with a chronic, severe, spinal cord injury (SCI). We propose to determine if daily gentamicin bladder instillations reduce the rate of symptomatic UTIs as well as the use of oral and intravenous antibiotics in adults with chronic SCI who have recurrent UTIs. This study will test the efficacy of intravesical gentamicin delivery and provide insights into the mechanisms that underlie the benefits of this local pharmacological effect for translation into the clinic.

Overall Hypothesis: The use of a daily gentamicin instillation treatment will significantly decrease the incidence of catheter-associated complications, such as chronic symptomatic urinary tract infections as well as improve urological outcomes, thus greatly enhancing the quality of life for individuals with bladder dysfunction.

Specific Aim 1: To assess the effects of gentamicin bladder instillation (saline instillation and no instillation will serve as controls) on:1) bacteriuria (number and species, antimicrobial resistant bacteria, urinary leukocytes, and urinary pH), 2) risk factors for developing UTI (over-distention of the bladder, high-pressure voiding, large post-void residuals, detrusor sphincter dyssynergia, presence of stones, and signs of hydronephrosis resulting from vesico-ureteral reflux), and 3) individual tolerability (blood pressure outcomes).

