1. Blinding Plan: This is a double-blind study whereby the investigators, research assistants, research nurse and participants will be blinded as to the drug treatment designation. Once participants have been assessed for eligibility and enrolled in the study, they will be randomized into 1 of 3 different groups. Participants randomized to either group I or II will be blinded to the intervention fantibiotic instillation in group I or placebo (saline alone) in group II]. Gentamicin sulfate will be prescribed for the research participants by the study physician or nurse practitioner and instilled under the direction of the research nurse. Thus, the participants in groups I and II will not be able to discern their assigned treatment. To ensure the double-blind, only the study physician or nurse practitioner as well as the pharmacy, all of whom are not associated with the data collection or data analysis, will be un-blinded. Note, the research nurse assisting participants with the instillation will be blinded. All participants will be identified by number and the instillation solutions (gentamicin or placebo) will be numbered with the pharmacy having access to the code specifying which instillations are active and which are placebo for each participant. The investigators and direct research team members will not be permitted to have knowledge of the group assignments. In the case of a drug related adverse event, the study physicians will evaluate the event and prescribe treatment that will minimize or completely resolve the event if minor or moderate in severity and it does not interfere with activities of daily living or quality of life (as determined by the participant). Should it be determined that the event has gotten worse, or if the participant can no longer tolerate the event, the study drug will be discontinued, and the participant will be terminated from study participation. There are no expected reasons to unmask the study treatment. The study physician or nurse practitioner will decide if the blind is to be broken or not. The blind will not "routinely" be broken when a serious adverse event (SAE) occurs. If an SAE is probably or definitely drug-related, the drug/placebo intervention will be stopped, and the participant treated appropriately. Emergency drug code envelopes will be created by the pharmacy at the study site. These will be labeled by participant randomization number and contain information, which will un-blind the treatment of the individual subject. These envelopes are to be used only in extreme emergencies, such as when an emergency situation exists in which the participant's treatment would be affected by knowledge of his drug therapy, and there is no time to contact the Medical Monitor. Note, that at the end of the study, participants will be un-blinded to the intervention designation by the study physician or nurse practitioner. If a participant was randomized to the no instillation group, however, he/she may re-enroll into the study and directly receive the gentamicin intervention and are not required to wait until the end of study, as all parties are un-blinded and aware of the treatment (standard of care) in this instance. All data from participants re-enrolling into the gentamicin-only group will be kept separate from those who are enrolled in the main study who are blinded.

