
The following participant withdrawal criteria may be implemented in determining when and how to withdraw participants from the trial/investigational product treatment.

Drug Discontinuation Criteria:

The subject's participation may be terminated for safety precautions based on any of the following by the study investigator. 1) Drug-related severe adverse event; 2) UTI requiring intravenous antibiotics; 3) Diagnosis of systemic absorption; 4) Diagnosis of nephrotoxicity; 5) Diagnosis of ototoxicity; 6) Diagnosis of renal failure

Temporary Discontinuation Criteria:

Situations of temporary discontinuation of study drug followed by subsequent resumption of study drug are: 1) Resolution of an adverse event, especially in cases where it is determined that the study drug was unlikely to have caused the event. 2) Resolution of a symptomatic UTI.

Withdrawal from Study:

A participant may withdraw from study participation at any time. Whatever data has been collected at the time of study termination will be evaluated by the PI for use in the final study database. If a participant is terminated from the study, the investigator will have the option to recruit an additional participant. Of withdraw from the study was due to an adverse event, participants will be followed until complete resolution of the adverse event that was possibly or definitely drug-related.

2. Statistical Plan: Data will first be summarized. We will use means with associated standard deviation, median with associated interquartile range and full range (min-max) to summarize continuous variables. Categorical variables will be summarized with frequency count and standard deviation. We will perform 2 types of analyses: pre-post differences within each group and between group comparisons of the differences. To evaluate the pre-post changes in each group, we will use paired t-test. To compare the changes between the 3 groups, we will use ANOVA test. If the ANOVA test yields significant results, we will perform follow-up 2 by 2 group comparisons using 2-sample t-tests. If the underlying assumptions of these tests are not satisfied, we will use the non-parametric equivalent tests instead.

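### The PI decides, with no stated criteria, whether a withdrawn or terminated participant's data are used, and no analysis population is defined; the likely bias is small and the fix is cheap

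*Combined protocol and SAP*

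**What the plan says.** The withdrawal rules stand in section II.B, between the Blinding Plan and the Statistical Plan. The lead-in describes criteria "in determining when and how to withdraw participants from the trial/investigational product treatment", which does not separate stopping the drug from leaving the trial. Under Drug Discontinuation Criteria, "participation may be terminated for safety precautions based on any of the following by the study investigator"; the second ground is "2) UTI requiring intravenous antibiotics". Temporary discontinuation is also allowed, for example until a symptomatic UTI resolves.

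Under Withdrawal from Study, the rule on data is "Whatever data has been collected at the time of study termination will be evaluated by the PI for use in the final study database". On replacement: "If a participant is terminated from the study, the investigator will have the option to recruit an additional participant". The only follow-up stated after withdrawal applies when an adverse event was the cause: "participants will be followed until complete resolution of the adverse event that was possibly or definitely drug-related".

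The Objectives (II.A) ask whether gentamicin instillations "reduce the rate of symptomatic UTIs as well as the use of oral and intravenous antibiotics in adults with chronic SCI". The Statistical Plan names summaries, paired t-tests, a three-group ANOVA and follow-up t-tests. It states no analysis population, no missing-data rule and no dropout allowance.

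**The concern.** In a randomised comparison, the person who sees the outcomes should not also choose, case by case, whose data count. Three features make that possible here. The Data Safety and Monitoring Plan has the PIs review all study data. The Blinding Plan treats the no-instillation arm as un-blinded to everyone, and that arm is the comparator in the between-group power calculation. One ground for termination is an event the trial is trying to prevent.

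With 12 per arm, one or two exclusions change an arm noticeably. If the decision were made after the outcome was known, the published text would not show what rule had been applied. It is also unclear whether a recruit added after a termination takes the terminated participant's place in the analysis.

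**Working it through.** **The plan's own figures.** The plan gives no number for this rule. Its power figures assume that all 12 per arm are analysed. With noncentral t, SD 1.7 and n = 12, the standard error is 1.7/√12 = 0.491.
- Paired difference 1.5: noncentrality 1.5/0.491 = 3.06 on 11 df, power 79.4% (stated 80%).
- Paired difference 2: 95.9% (stated 97%).
- Two-sample unequal-variance test, difference 2, SDs 1.7 and 0: 95.9% (stated 96%).
- With 11 per arm, the first and third fall to 75.1% and 93.9%.

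**How often the case could arise.** The risk list for gentamicin instillation and associated assessments puts an IV-treated UTI under Rare, defined as 0-10%. Assume that this applies per participant in every arm. The chance of at least one case in 36 is 1 − (1 − q)^36: 30% at q = 1%, 84% at 5%, 98% at 10%. The expected number is 36q, or 0.4 to 3.6.

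**Size of the shift.** Assumptions not in the plan: Poisson UTIs at 4 per year, and each UTI independently needs IV treatment with probability p. The period of 80 days is from Screening and Enrollment (III.A).
- Mean count: μ = 4 × 80/365 = 0.877.
- If a share s has at least one IV-treated UTI, then s = 1 − exp(−μp), so p = −ln(1 − s)/μ. At s = 10%, p = 0.105/0.877 = 0.120.
- Among those with no IV-treated UTI the mean is μ(1 − p). The shift is therefore μp = −ln(1 − s) at any UTI rate: 0.02, 0.05 and 0.11 UTI at s = 2%, 5% and 10%.
- The mean falls from 0.877 to 0.772, or 12% (16% at 3 per year, 8% at 6 per year).

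**Type I error** (simulated, 12 per arm, s = 10%, no true effect, dropped from gentamicin only): two-sample test against the open arm 5.3%, against 5.0% with nobody dropped; paired test 5.3% against 4.8%. Dropping by the same rule in both arms being compared gives a shift of 0.00 and error of 4.8-5.0%.

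**If gentamicin halves the rate** (assumed; s = 10% in controls, same p per UTI), the true difference is 0.877 − 0.438 = 0.44 UTI. After exclusion:

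| Dropped from | Comparison | Calculation | Difference |
|---|---|---|---|
| Open arm only | gentamicin vs open | 0.772 − 0.438 | 0.33 (24% smaller) |
| Both instillation arms | gentamicin vs open | 0.877 − 0.438 × 0.88 | 0.49 (12% larger) |
| Both instillation arms | gentamicin vs saline | (0.877 − 0.438) × 0.88 | 0.39 (12% smaller) |
| All arms | gentamicin vs open | (0.877 − 0.438) × 0.88 | 0.39 (12% smaller) |

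**The case against.** **Blinding.** "The investigators and direct research team members will not be permitted to have knowledge of the group assignments". This stands for gentamicin against saline and makes exclusion from gentamicin alone unlikely. It does not cover the open arm, and it does not stop selection on the outcome itself.

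**Rarity and options.** Termination for an IV-treated UTI is permitted, not required, and temporary discontinuation keeps many symptomatic participants in the study. IV use is named as an outcome only in the Objectives; Hypothesis 1.1 names oral courses. All this stands and is why the expected size is small. However, the data rule covers every withdrawal and termination, not only this ground, and an IV-treated UTI that meets the study's definition also counts as symptomatic.

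**Oversight.** The Medical Monitor reviews drop-outs and protocol deviations each year, and the written report goes to the IRB. That is partial protection, but it does not fix in advance whose data are analysed. An additional participant most naturally means one added, so that part of the fix is largely clarification.

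**A stronger reading.** A reader might infer that the rule seriously inflates false positives or favours gentamicin. The documents do not support that. Dropping the single worst of 12 gentamicin results (normal changes, SD 1.7) gives a shift of 0.25 UTI and about 7% error, but only for a t-test run without the ANOVA first. With the planned ANOVA gate, gentamicin against open has an error just under 4%, compared with 2.5% when nobody is dropped. The scenario also needs a PI who can identify gentamicin participants. Likewise, a fall in power from 79% to 69% after dropping the worst control needs a control SD of 1.7, whereas the plan assumes 0. These are outer limits, on the plan's 6-month scale, and should not be combined with the 80-day figures.

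**Conclusion.** The point holds in a limited form. The plan states a discretionary rule on data use where it should state an analysis set, and the rule permits selection on the outcome. Nothing in the documents shows that such selection is intended.

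At the top of the Rare band the shift is about 0.11 UTI, and type I error barely moves. The direction depends on who is dropped and on the comparison: against the open arm, exclusion can exaggerate or hide an effect; against saline, dropping from both instillation arms only shrinks a true one. These sizes rest on the Poisson model, on the Rare band applying in every arm, and on every affected participant being excluded. The 4 per year and the halved rate are also assumptions, but the 0.11 does not depend on the UTI rate.

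A reader might also infer a flat contradiction between the withdrawal criteria and the urine-culture section, which lets the clinician recommend continuing during systemic antibiotics. Both are permissive and can coexist. What needs reconciling is whether stopping the drug ends participation. The Blinding Plan says that it does for a worsening or intolerable drug-related event; elsewhere it is left open.

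Severity: minor; a cheap improvement.

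**What to change.** Leave the safety stopping criteria as they are.

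1. Replace the PI-discretion sentence with: *All randomised participants are analysed in their assigned arm using all data collected up to withdrawal, including any UTI that led to termination.* Data from re-enrolled participants stay separate, as the Blinding Plan already says.
2. State that any additional recruit is added and does not displace a terminated participant.
3. Report by arm the number of and reasons for terminations and missing post-intervention values.
4. Optionally, prespecify a sensitivity analysis of UTI counts by arm with log days observed as offset. The planned tests stay primary.
5. Reconcile the Blinding Plan, the withdrawal criteria and the urine-culture section on whether stopping the study drug ends participation. Where participation continues, record UTIs and antibiotic courses to the planned end unless consent is withdrawn.

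**Cost:** a few sentences, one reporting table and optionally one model. Estimates will include time off instillation. Continued follow-up needs urine specimens as well as contacts, because the UTI definition requires urine tests and culture. If every IV-treated UTI led to stopping, that is an expected 0.4 to 3.6 of 36 participants (1% to 10%), plus any stopped for other reasons.

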Hypothesis 1.1: Bladder instillation with a gentamicin antimicrobial solution will result in significantly decreased episodes of symptomatic UTIs, fewer courses of oral antibiotics, and a reduction of multi-drug resistant organisms on urine culture, as compared to controls.

Hypothesis 1.2: Bladder instillation with a gentamicin antimicrobial solution will decrease detrusor spasms, increase bladder compliance as well as mitigate the rapid rise in systolic blood pressure (autonomic dysreflexia) evidenced during cystometry as compared to controls.

B. Study Design/Methodology

In a randomized, double-blind, prospective study, we will compare the long-term effects (80 daily sessions, 2x per day) of a bladder instillation protocol in 3 groups of individuals (n=36; 3 groups of 12) with chronic SCI receiving either:

1) gentamicin bladder instillation

2) saline installation

3) no instillation (catheter clamping only in those with suprapubic catheters for the duration of the irrigation time frame - refer to Fig. 2 timeline).

The control groups will also serve to address the question of whether bacteria already colonized in the bladder would also provide a protective role in preventing more pathogenic bacteria or other organisms, such as yeast, which also colonize the bladder. Research participants will complete the 80 sessions of twice per day instillations initially in the Urogenital and Bowel Laboratory, where blood pressure and heart rate will be continually monitored (approximately 1-2 weeks). Once safe pressures are established, the remaining instillations may be completed in the home setting. A major issue confounding validity of a clinical trial is compliance. Given that this study assesses the long-term outcomes of daily bladder instillations and allows for the twice-daily instillations to be conducted in the home-setting, it is possible that participants may not be fully

compliant with respect to study duration and frequency of instillations. In an effort to improve the applicability of the study results to individual participants and mitigate non-compliance, our research nurse will guide participants through all aspects of the instillation procedure to ensure that they are fully independent. At-home blood pressure monitoring during instillation times is automatically recorded and will be an additional step in monitoring protocol adherence.

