We propose to use a sample size of 36 (12 in each of the three arms). Cox et al., (46) has found that the use of intravesical gentamicin was associated with a reduction of a median 3 symptomatic UTIs in 6 months in 22 patients. Using the formulas proposed by Hozo et al., (47) we estimated the corresponding standard mean change to be 2.48 with a standard deviation of 1.7. Assuming the same standard deviation in our data, a sample size of 12 achieves 80% power to detect a mean of paired differences of as low as 1.5 symptomatic UTIs for the gentamicin group with a significance level of 0.05 using a two-sided paired ttest (48, 49). We expect to observe a drop of at least 2 symptomatic UTIs in 6 months. With the same setting, i.e. SD = 1.7, a sample size of 12 achieves 97% power to detect that. Our study will compare changes between the gentamicin instillation, the saline instillation and the no-instillation groups. We will use the comparison between the gentamicin and the non-instillation group to estimate the power. The estimated effect of gentamicin is a reduction in symptomatic UTIs of 2 with a standard deviation of 1.7 (described above) and we assume no change for the non-instillation group (mean reduction of 0 with a standard deviation of 0). With these values, sample sizes of 12 (gentamicin) and 12 (no-instillation) achieve 96% power to reject the null hypothesis of equal means with a significance level of 0.050 using a two-sided two-sample unequal-variance t-test (48-51). The power analysis was performed in PASS 14 Power Analysis and Sample Size Software (NCSS, LLC. Kaysville, Utah, USA, ncss.com/software/pass).

Experimental Outcomes – Research Procedures

1. Intravesical Gentamicin Sulfate Instillation

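### The Statistical Plan does not say whether the within-arm paired tests or the between-arm ANOVA decides efficacy, and the ANOVA of changes does not use baseline as a covariate

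*Combined protocol and SAP*

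**What the plan says.** The Statistical Plan (section II.B.2) announces two analyses side by side: "We will perform 2 types of analyses: pre-post differences within each group and between group comparisons of the differences". For the first, "To evaluate the pre-post changes in each group, we will use paired t-test". For the second, "To compare the changes between the 3 groups, we will use ANOVA test", with two-sample t-tests to follow only if the ANOVA is significant. The fallback is "If the underlying assumptions of these tests are not satisfied, we will use the non-parametric equivalent tests instead". Neither analysis is called primary, and no baseline covariate is mentioned.

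Other sections bear on which test is meant to decide:

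- Objectives (II.A): "This study will test the efficacy of intravesical gentamicin delivery".
- Hypothesis 1.1 expects "a reduction of multi-drug resistant organisms on urine culture, as compared to controls". Hypothesis 1.2 is also worded against controls.
- Sample-size text (II.B.2): "Our study will compare changes between the gentamicin instillation, the saline instillation and the no-instillation groups". The same text first claims "80% power to detect a mean of paired differences of as low as 1.5 symptomatic UTIs for the gentamicin group", then 97% power for a paired drop of 2. Only after that does it give 96% for gentamicin against no instillation.
- Inclusion Criteria (III): entry requires at least 3 UTIs in the past year or at least 2 in the past 6 months.

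The Statistical Plan sets no window for the baseline UTI count. Figure 2 gives screening 5 days, so that count must be largely retrospective and can overlap the period used for selection.

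**The concern.** People admitted because they recently had many UTIs will, on average, tend to have fewer afterwards even if nothing is done. A paired test in the gentamicin arm counts that fall as benefit. The randomised comparison does not, because all three arms are selected in the same way. If no deciding test is named, a report could rest an efficacy claim on a significant drop within the gentamicin arm while the comparison with controls shows nothing.

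A smaller issue concerns the between-arm test. It subtracts baseline instead of adjusting for it, which gives up precision that a trial with 12 per arm could use.

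The selection argument applies to UTI counts. It has not been shown for the urodynamic or blood pressure outcomes.

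**Working it through.** **The plan's own power figures** (n = 12, SD of change 1.7, two-sided 0.05, exact noncentral t)

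- Standard error of a paired change: 1.7/√12 = 0.491.
- Drop of 1.5: noncentrality 1.5/0.491 = 3.06 on 11 df, power 79.4% (stated 80%).
- Drop of 2: noncentrality 2/0.491 = 4.08 on 11 df, power 95.9% (stated 97%).
- Gentamicin against no instillation, with the plan's control SD of 0: standard error √(1.7²/12 + 0) = 0.491, Satterthwaite df 11, power 95.9% (stated 96%).

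The between-arm figure has the same standard error and df as the paired test. The power statement therefore does not show which test is meant to decide.

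**Simulation inputs**

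- From the documents: 12 per arm, the entry rule, 80 days of treatment (Screening and Enrollment), and 2.5 UTIs a year (Prevalence section, a figure for people with SCI generally).
- Assumed: 4 and 6 UTIs a year as alternatives; gamma-distributed personal rates with shape 1, 2 or 4; Poisson counts; no UTI in the last 14 days, as a proxy for the two-week antibiotic exclusion; baseline count over the last 6 months; everyone followed for the full 80 days.
- On-study count scaled to 6 months: factor 0.5 × 365.25/80 = 2.28.
- Paired test: t = mean change/(SD/√12) on 11 df, counted when it favours gentamicin (nominal 2.5%). ANOVA of changes: F on 2 and 33 df. ANCOVA of the on-study value on arm and baseline: F on 2 and 32 df. 20,000 trials per setting, 8,000 for rank tests.

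**No treatment effect**

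| UTIs/year | Paired t significant | Wilcoxon significant | Paired t significant, ANOVA not | Paired t, 80-day baseline |
|---|---|---|---|---|
| 2.5 | 10-16% | 11-16% | 8-14% | 4-6% |
| 4 | 6-7% | 7% | 5-6% | about 2% |
| 6 | 4% | 4-5% | about 3% | about 1% |

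If rates did not vary between people, the paired figure at 2.5 a year would be 22%. Including that case, the mean fall per 6 months is 0.34-0.62 UTIs at 2.5 a year, 0.16-0.23 at 4, and about zero (-0.10 to 0.01) at 6. The small excess at 6 a year is therefore not a selection effect. It more likely reflects skewed, scaled-up counts in 12 people. Type I error is 4.4-5.2% for the ANOVA of changes and 4.4-5.1% for ANCOVA.

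**Precision of the between-arm test, assumed rate ratio 0.4 in gentamicin and 1 in both controls**

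| UTIs/year | ANOVA of changes | ANCOVA |
|---|---|---|
| 2.5 | 16-21% | 20-25% |
| 4 | 23-28% | 29-32% |
| 6 | 32-34% | 38-39% |

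The gain is about 3-8 points. In rank form at 2.5 a year, Kruskal-Wallis on changes has 16-21% power and Quade's rank ANCOVA 23-28%. Quade's type I error is 4.5-5.4%.

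**Continuous outcomes.** With equal pre and post variances and pre-post correlation r, the change score has variance 2s²(1 - r) and the ANCOVA residual s²(1 - r²), a ratio of (1 + r)/2. For a pairwise contrast with difference 2 and change SD 1.7, unadjusted power is 80%. ANCOVA gives 93%, 89%, 85%, 83% and 81% at r = 0.3, 0.5, 0.7, 0.8 and 0.9. At r = 0.9 the gain is under 1 point (80.8% against 80%).

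**The case against.** The strongest reply is that the intended contrast is already visible. The hypotheses are worded against controls, the sample-size text says changes will be compared between groups, and nowhere is a within-arm result said to establish efficacy. The protocol also calls itself a feasibility study. This stands as far as intention goes. It does not settle the role of three planned paired tests, one of which is powered, in a study that also says it will test efficacy.

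Second, the size of the selection effect rests on inputs the documents do not give. The 2.5 a year is not a rate for people enrolled under this entry rule. At that rate, simulated baselines average only 2.05-2.45 UTIs per 6 months, so the plan's expected drop of at least 2 would mean removing 82-98% of them (2/2.45 to 2/2.05). Higher rates fit that expectation better, and there the excess is small. Pairing a 6-month baseline with an 80-day follow-up is also an assumption. All of this stands, and it is why the result is given as a range.

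Third, the ANOVA of changes is valid and the ANCOVA gain is modest. That is also true, but the gain is nearly free because the plan already needs the baseline value.

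**Conclusion.** The point holds as a gap in specification with a modest loss of precision, and it should be corrected. The plan names no deciding test. With no effect, the gentamicin paired test alone would favour gentamicin in about 10-16%, 6-7% or 4% of trials at 2.5, 4 or 6 UTIs a year, and would do so without a significant ANOVA in about 8-14%, 5-6% or 3%. These figures depend on the assumed rates, the between-person variation and the 6-month baseline window. With an equal 80-day window the excess largely disappears.

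Three stronger readings are tempting and are not supported:

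- A reader might infer that the trial relies on paired tests for efficacy. The hypotheses and the sample-size text point the other way.
- A reader might infer that the unadjusted ANOVA is biased. Its type I error is about 5%; it only loses precision.
- A reader might take disagreement between the two tests under a real effect as evidence of harm. At rate ratio 0.4 the paired test is significant and the ANOVA is not in 40-61% of trials. There gentamicin truly works, and the disagreement mostly reflects the ANOVA's low power of 16-34%.

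**What to change.** In the Statistical Plan:

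1. State that the randomised between-arm comparison is the only efficacy test, and report within-arm pre-post changes descriptively.
2. Replace the ANOVA of changes with ANCOVA of the on-study value on arm and baseline value, for continuous outcomes and for UTI and antibiotic-course counts. Keep the overall arm test as the gate to pairwise contrasts.
3. Where the assumptions fail, use Quade's rank ANCOVA in place of Kruskal-Wallis on changes.
4. Record baseline UTI and antibiotic-course counts over one fixed window for every participant. The entry rule only requires that a threshold is met.
5. Add a sensitivity analysis for exposure that stops early, for example a count model with an exposure offset. The discontinuation criteria allow participation to end because of a UTI, so exposure can depend on the outcome. The simulations gave everyone the full 80 days and do not test this.

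The cost is the wording, the fixed-window count, and one error degree of freedom (36 - 3 = 33 falls to 32). Treatment, visits and sample size do not change.
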